### **8.5 Duration of Therapy**

Duration of therapy will depend on individual response, evidence of disease progression and tolerance. In the absence of treatment delays due to adverse events, treatment may continue until one of criteria in Section 8.7 applies.

### **8.6 Duration of Follow-Up**

Participants will be followed for 30 days for toxicity after the final dose of study drug. The 30 day follow-up can be done by phone or through a clinic visit. Patients who at the treatment completion visit have an ongoing serious adverse event or an adverse event leading to treatment discontinuation will be followed every 3 months until the event resolves, the investigator assesses the event as stable, or the patient is lost to follow-up. Participants will also be followed for disease progression by chart review yearly for 3 years from the date of last study drug administration. If the patient is no longer coming to the institution for care, then the patient may be called as needed for follow-up.

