- i Tumor assessment should be performed approximately every 3 cycles (up to -5 days) while on study treatment (i.e. on or up to 5 days prior to Day 1 of Cycles 4, 7, 10 etc) and at End-of-treatment visit if not obtained within the past 6 weeks. Scans should consist of CT scan of the chest, abdomen, and pelvis and a bone scan at baseline. Of note, if the prior bone scan did not show metastases, it does not need to be repeated if the bone scan was obtained within 8 weeks of CID1. Subsequent scans should consist of CT chest, abdomen and pelvis, and bone scan if bone metastases were present on the baseline studies. MRI is also an acceptable form of imaging. At the end of treatment, all scans (baseline and through disease progression) should be sent on a CD to the Vanderbilt Cancer Imaging Support Laboratory for central review and assessment. See Section 12.6 for details and address.
- j Archived tumor biopsy specimen: Archived biopsy block (unstained slides) will be requested at the time of registration prior to initiation of treatment. See Section 11.1 for details. If archived tissue is not available, the VICC coordinating center should be contacted.
- k After signing consent, a fresh tumor biopsy from a metastatic site amenable to a reasonably safe biopsy will be obtained prior to day 1 and upon progression of disease (see Section 11). The second biopsy will not be required for patients who are removed from study for reasons other than disease progression. A patient who undergoes a research biopsy procedure for the purpose of this protocol, in whom inadequate tissue is obtained, is not obligated to undergo a repeat biopsy.

- l After cycle 6, at the discretion of the treating physician, carboplatin can be stopped and atezolizumab can be continued as a single agent.
- m The dose of steroids before each carboplatin injection should be recorded. Prohibited medications (section 8) must be discontinued at least 7 days prior to initiation of study drug (C1D1).
- n 1, 2, and 3 year follow-up can be done by phone or chart review to document survival status, and if applicable, the date of death and cause of death. Surveillance for Adverse Events of Special Interest (AESIs) (see section 13.5.12) should be included.
- o Biopsy questionnaire should be filled out by the patient on C2D1. Form can be found in the packet of supplemental forms.  

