### 8.4 Cross-over post-progression

Patients who are randomized to carboplatin alone can cross over to receive atezolizumab upon disease progression based on clinical progression or radiographic progression. Patients who are randomized to carboplatin alone and who discontinue carboplatin for toxicity cannot cross over to receive single agent atezolizumab. There may be exceptions to this based on discussion with the Protocol Chair. However, patients on the carboplatin + atezolizumab arm can continue to receive single agent atezolizumab if they discontinue carboplatin due to toxicity. Patients who cross over to receive atezolizumab will follow the assessments and procedures as outlined in the study calendar. The duration of each cycle will continue to be 21

days and the cycle numbers will "reset" to 1 and will be followed by the "X" suffix (e.g., Cycles 1X, 2X, etc.). Crossover therapy (atezolizumab) must begin no later than 21 days after the clinic visit at which progression is determined.

Patients must have labs and procedures performed as outlined in the cross-over study calendar and must meet the values as described in the Inclusion Criteria, prior to receiving atezolizumab based on assessments and procedures performed within 21 days prior to Day 1 of Cycle 1X. Labs and procedures not included in the cross-over study calendar do not have to be repeated. Patients must also agree to a tumor biopsy, as outlined in the eligibility criteria, prior to initiating atezolizumab. Patients will receive crossover treatment until progression, intolerable toxicity, or elective withdrawal from the study. Patients who cross over will be evaluated with radiologic assessments every 3 cycles until disease progression.

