### **8.7 Criteria for Removal from Study**

Patients will be removed from study when any of the criteria listed below apply. All patients who initiate protocol treatment will be included in the overall evaluation of response (intent-to-treat analysis). All reasons for discontinuation of therapy should be documented clearly in the medical record.

If a subject discontinues or withdraws from the study, every reasonable attempt will be made to get a tissue/tumor biopsy, along with blood, at the end of treatment, if the subject is able and willing.

Patients may be withdrawn from the study if they experience any of the following:

- Disease progression, per investigator assessment by RECIST (or irRECIST for atezolizumab arm)
- Intolerable toxicity to atezolizumab or carboplatin. Patients assigned to carboplatin + atezolizumab who experience toxicity to atezolizumab or carboplatin can continue on study with single agent carboplatin or atezolizumab, respectively, at the discretion of the treating physician. Patients will be followed for disease progression and should continue radiologic assessments every 3 cycles as per the study.

Other reasons for patient discontinuation may include, but are not limited to, the following:

- Non-compliance with the study protocol, including, but not limited to not attending the majority of scheduled visits. The Protocol Chair will determine when non-compliance should lead to removal from study. Note: The patients will still be included in the overall evaluation of response (intent-to-treat analysis).
- Patient personal decision. The reason for discontinuation from the study must be documented. The patients will be included in the overall evaluation of response (intent-to-treat analysis) if any protocol therapy was administered prior to withdrawal.
- If the patient becomes pregnant
- Patient is lost to follow-up
- Study is terminated for any reason

The investigator has the right to discontinue a patient from the study for any medical condition that the investigator determines may jeopardize the patient's safety if he or she continues in the study; for reasons of noncompliance (e.g., missed doses, visits); or if the investigator determines it is in the best interest of the patient. The Protocol Chair should be notified in such cases.

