## 17.2 Sample Size/ Accrual Rate

The sample size estimation was completed using the log-rank test. A total sample size of 106 (n=53 in each arm) provides 80% power to detect a 1.5 month improvement in the median PFS, i.e. 2.9 months vs. 4.4 months, with a one-sided significance level equal to .10 (type I error). This estimation is based on the assumptions that accrual time is 24 months, additional follow-up time is 12 months, and the ratio randomization is 1:1.

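### Rules for scanning after study drug stops contradict each other, and on one reading a carboplatin toxicity stop makes primary PFS ascertainment differ by arm

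*Combined protocol and SAP*

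**What the plan says.** **Progression event.** Section 12 makes a tumour assessment showing RECIST progression the progression event for PFS.

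**When scans happen.** Footnote i of the Section 7.1 calendar schedules assessments about every 3 cycles (9 weeks) for patients on study drug. It adds one at the end-of-treatment visit if none was done in the previous 6 weeks. The calendar shows no tumour assessment in the 30-day or yearly columns.

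**After the last dose.** Section 8.6: "Participants will also be followed for disease progression by chart review yearly for 3 years from the date of last study drug administration". Footnote n of Section 7.1 describes the yearly contact differently: "1, 2, and 3 year follow-up can be done by phone or chart review to document survival status", with date and cause of death and adverse events of special interest. It does not mention progression.

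**After a carboplatin toxicity stop.** Section 8.4, control arm: "Patients who are randomized to carboplatin alone and who discontinue carboplatin for toxicity cannot cross over to receive single agent atezolizumab" (the Protocol Chair may allow exceptions). Section 8.4, combination arm: "patients on the carboplatin + atezolizumab arm can continue to receive single agent atezolizumab if they discontinue carboplatin due to toxicity".

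**Text pointing the other way.** The Schema and Section 2 put scans at 9-week intervals without limiting them to treated patients. The intolerable-toxicity bullet of Section 8.7 ends: "Patients will be followed for disease progression and should continue radiologic assessments every 3 cycles as per the study". That sentence names no arm.

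**The concern.** Consider two patients with stable disease who both stop carboplatin for the same toxicity. The combination patient can stay on atezolizumab, and so on the scan calendar, until RECIST progression. The control patient normally has no study drug left. Under footnote i and Section 8.6 she has at most an end-of-treatment scan, then a yearly chart review or phone contact. Neither of those is itself a RECIST assessment.

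The primary endpoint could then be ascertained differently by arm, in patients selected by toxicity. The trial is open-label and Section 17 has no rule for dating or censoring PFS in these patients. A rule chosen after the data are seen would be hard to defend.

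**Working it through.** **1. The plan's own figure.** Section 17.2: "A total sample size of 106 (n=53 in each arm) provides 80% power to detect a 1.5 month improvement in the median PFS", that is "2.9 months vs. 4.4 months", by log-rank test at one-sided 0.10, with 1:1 allocation, 24 months of accrual and 12 months of further follow-up.

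- Exponential hazard ratio = 2.9/4.4 = 0.659; ln(4.4/2.9) = 0.417.
- Events needed (Schoenfeld) = 4 × (1.2816 + 0.8416)² / 0.417² = 104.
- Event probability with uniform accrual A = 24, follow-up F = 12 and λ = ln 2/median: 1 − [exp(−λF) − exp(−λ(A+F))]/(λA) = 0.990 control, 0.961 combination, mean 0.976.
- N = 104/0.976 ≈ 107, against 106 stated. At N = 106, expected events are 103.4 and power is Φ(√(103.4/4) × 0.417 − 1.2816) = 0.799.

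The figure is reproduced. It requires nearly every patient to be followed to an event, and Section 17.2 states no allowance for lost PFS ascertainment.

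**2. What an arm difference could do.** The documents give no rate of toxicity stops before progression, so 5%, 10% and 20% of control patients are assumed. The simulation used 53 patients per arm, exponential PFS at the planned medians, progression seen at 9-week scans, stops uniform over cycles 1 to 6, and combination patients remaining on scans (1,500 runs per case). Patients who had already progressed by their stop time were unaffected. Type I error was simulated with both medians at 2.9 months. Two handling rules were tried, because the plan gives none.

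| Handling of affected control patients | Assumed stop rate | Power | One-sided type I error | Mean events at planned medians |
|---|---|---|---|---|
| None affected: all stay on 9-week scans | 0% | 0.775 | 0.097 | 102.9 |
| Progression dated at yearly review | 5% | 0.707 | 0.063 | 102.7 |
| | 10% | 0.607 | 0.026 | 102.6 |
| | 20% | 0.445 | 0.019 | 102.3 |
| Censored at last or end-of-treatment scan | 5% | 0.808 | 0.107 | 101.3 |
| | 10% | 0.791 | 0.130 | 99.9 |
| | 20% | 0.786 | 0.123 | 96.9 |

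The simulation standard error is about √(0.1 × 0.9/1500) = 0.008 for type I error and √(0.775 × 0.225/1500) = 0.011 for power. The value 0.107 is therefore within error of the nominal 0.10; 0.130 and 0.123 are not.

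**3. Reading the table.** Dating at yearly review keeps nearly all events but places some late in the control arm, which works against the combination. Censoring loses 1.6, 3.0 and 6.0 events (102.9 minus 101.3, 99.9 and 96.9), leaves power about where it was and moves type I error slightly upward. The unwritten rule decides both direction and size.

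**The case against.** The strongest reply is that the documents already keep everyone on scans. The Schema and Section 2 count in weeks, so an untreated patient can follow them, and the last sentence of the Section 8.7 toxicity bullet names no arm. This reading is open, so the defect is a contradiction and not a plain absence. It does not settle the matter. The Section 8.7 sentence directly follows one about combination patients continuing a single drug, and it counts in cycles. Footnote i and Section 8.6 say something different, and sites could follow either. The Section 12.3.5 note urging documentation of progression after discontinuation covers symptomatic deterioration only and sets no schedule.

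The arm contrast is also not absolute. Section 8.7 leaves continuation of the second drug to the treating physician, and a combination patient who stops both drugs has the same gap. Section 9.3.1.1 ends all study treatment after a chemotherapy hold of more than 42 days, with no exception for the combination arm. That rule must be reconciled with Sections 8.4 and 8.7.

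Finally, a yearly chart review can recover the dates of scans done in between, and the calendar labels tumour assessments standard of care. This stands: no section says progression is dated on the day of review, so the yearly-dating rows show a possible consequence, not the plan's rule.

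**Conclusion.** The point holds as an unresolved contradiction. If footnote i and Section 8.6 govern, primary PFS is ascertained differently by arm after a carboplatin toxicity stop, once the end-of-treatment scan is past. This is more than missing detail, because following those passages as written changes how the primary endpoint is measured.

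A reader might infer three stronger things that the documents do not support:

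- *That control patients have no further scheduled scan.* Footnote i provides an end-of-treatment scan in both arms, and Sections 2 and 8.7 can be read as requiring more.
- *That the gap lengthens control PFS and hides a benefit.* That follows if progression is dated at review. Censoring at the last scan gives a different result.
- *That power falls to 77-78% through lost events.* Taking 10-20% of 53 control patients as lost gives 103.4 − 5.3 = 98.1 and 103.4 − 10.6 = 92.8 events, with power 0.78 and 0.77. This counts every stop as a lost event. With stops spread over cycles 1 to 6, some patients progress first, and the simulated loss at those rates is 3.0 to 6.0 events.

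The sizes rest on assumed stop rates, exponential PFS and stopping unrelated to prognosis. The contradiction rests on none of these.

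**What to change.** 1. Reconcile Sections 8.6 and 8.7 and footnotes i and n of Section 7.1 with Section 2. All randomized patients in both arms without RECIST progression should keep the same 9-week standard-of-care tumour assessments, read by RECIST, until progression, death or withdrawal of consent, whatever their study-drug status.
2. At minimum, collect the dates and RECIST readings of standard-of-care scans done after stopping and the date of any new anti-cancer therapy. Add progression to footnote n so that it matches Section 8.6.
3. In Section 17, date progression at the scan that shows it, not at the chart review. State the PFS censoring rule, including for new anti-cancer therapy, and add a sensitivity analysis for patients who stop treatment without progression.
4. Reconcile the 42-day rule in Section 9.3.1.1 with Sections 8.4 and 8.7, since it determines who remains on the scan calendar.

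The sample size stays at 106. With everyone on 9-week scans the simulation gives power 0.775 and one-sided type I error 0.097. The cost is amendment wording, a few case report form fields and modest extra data entry at sites.

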### **8.7 Criteria for Removal from Study**

Patients will be removed from study when any of the criteria listed below apply. All patients who initiate protocol treatment will be included in the overall evaluation of response (intent-to-treat analysis). All reasons for discontinuation of therapy should be documented clearly in the medical record.

If a subject discontinues or withdraws from the study, every reasonable attempt will be made to get a tissue/tumor biopsy, along with blood, at the end of treatment, if the subject is able and willing.

Patients may be withdrawn from the study if they experience any of the following:

- Disease progression, per investigator assessment by RECIST (or irRECIST for atezolizumab arm)
- Intolerable toxicity to atezolizumab or carboplatin. Patients assigned to carboplatin + atezolizumab who experience toxicity to atezolizumab or carboplatin can continue on study with single agent carboplatin or atezolizumab, respectively, at the discretion of the treating physician. Patients will be followed for disease progression and should continue radiologic assessments every 3 cycles as per the study.

Other reasons for patient discontinuation may include, but are not limited to, the following:

- Non-compliance with the study protocol, including, but not limited to not attending the majority of scheduled visits. The Protocol Chair will determine when non-compliance should lead to removal from study. Note: The patients will still be included in the overall evaluation of response (intent-to-treat analysis).
- Patient personal decision. The reason for discontinuation from the study must be documented. The patients will be included in the overall evaluation of response (intent-to-treat analysis) if any protocol therapy was administered prior to withdrawal.
- If the patient becomes pregnant
- Patient is lost to follow-up
- Study is terminated for any reason

The investigator has the right to discontinue a patient from the study for any medical condition that the investigator determines may jeopardize the patient's safety if he or she continues in the study; for reasons of noncompliance (e.g., missed doses, visits); or if the investigator determines it is in the best interest of the patient. The Protocol Chair should be notified in such cases.

## 9. EXPECTED TOXICITIES AND DOSING DELAYS/DOSE MODIFICATIONS

### 9.1 Anticipated Toxicities of atezolizumab (Atezolizumab) and Dose Modifications

Toxicities associated or possibly associated with atezolizumab treatment should be managed according to standard medical practice. Additional tests, such as autoimmune serology or biopsies, should be used to evaluate for a possible immunogenic etiology, when clinically indicated. Although most immune-mediated adverse events observed with atezolizumab have been mild and self-limiting, such events should be recognized early and treated promptly to avoid potential major complications. Discontinuation of atezolizumab may not have an immediate therapeutic effect, and in severe cases, immune-mediated toxicities may require acute management with topical corticosteroids, systemic corticosteroids, or other immunosuppressive agents.

The investigator should consider the benefit–risk balance for a given patient prior to further administration of atezolizumab. In patients who have met the criteria for permanent discontinuation, resumption of atezolizumab may be considered if the patient is deriving benefit and has fully recovered from the immune-mediated event. Patients can be re-challenged with atezolizumab only after approval has been documented by both the investigator (or an appropriate delegate) and the Medical Monitor. Guidelines for managing patients who experience selected adverse events are provided in the following sections. Management guidelines are presented by adverse event severity based on the National Cancer Institute (NCI) Common Terminology Criteria for Adverse Events (CTCAE) and in some instances may vary by CTCAE version (4.0 vs. 5.0).

#### Management Guidelines for Renal Events

Event	Management
Renal event, Grade 1	
 
• Continue atezolizumab.
 
• Monitor kidney function, including creatinine, closely until values resolve to within normal limits or to baseline values.
 

Renal event, Grade 2	
 
• Withhold atezolizumab for up to 12 weeks after event onset. a
 
• Refer patient to renal specialist.
 
• Initiate treatment with corticosteroids equivalent to 1-2 mg/kg/day oral prednisone.
 
• If event resolves to Grade 1 or better, resume atezolizumab. b
 
• If event does not resolve to Grade 1 or better while withholding atezolizumab, permanently discontinue atezolizumab and contact Study Chair. c
 

Renal event, Grade 3 or 4	
 
• Permanently discontinue atezolizumab and contact Study Chair.
 
• Refer patient to renal specialist and consider renal biopsy.
 
• Initiate treatment with corticosteroids equivalent to 1-2 mg/kg/day oral prednisone.
 
• If event does not improve within 48 hours after initiating corticosteroids, consider adding an immunosuppressive agent.
 
• If event resolves to Grade 1 or better, taper corticosteroids over <math>\geq 1</math> month.
 

---------------------------	---

- a Atezolizumab may be withheld for a longer period of time (i.e., > 12 weeks after event onset) to allow for corticosteroids (if initiated) to be reduced to the equivalent of  $\leq 10$  mg/day oral prednisone. The acceptable length of the extended period of time must be agreed upon by the investigator and the Study Chair.
- b If corticosteroids have been initiated, they must be tapered over  $\geq 1$  month to the equivalent of  $\leq 10$  mg/day oral prednisone before atezolizumab can be resumed.
- c Resumption of atezolizumab may be considered in patients who are deriving benefit and have fully recovered from the immune-mediated event. Patients can be re-challenged with atezolizumab only after approval has been documented by both the investigator (or an appropriate delegate) and the Study Chair.

## 9.2 General Guidelines for Dosage Modification and Treatment Interruption or Discontinuation

Atezolizumab treatment will be given as long as the patient continues to experience clinical benefit in the opinion of the investigator until the earlier of unacceptable toxicity, symptomatic deterioration attributed to disease progression, or any of the other reasons for treatment discontinuation listed above.

There will be no dose reduction for atezolizumab in this study. **Patients may temporarily suspend study treatment for up to 84 days beyond the scheduled date of delayed infusion if study drug-related toxicity requiring dose suspension is experienced.** If atezolizumab is held because of AEs for > 84 days beyond the scheduled date of infusion, the patient will be discontinued from atezolizumab and will be followed for safety and efficacy as specified in the protocol.

If a patient must be tapered off steroids used to treat AEs, atezolizumab may be held for additional time beyond 84 days from the scheduled dose until steroids are discontinued or reduced to a prednisone dose (or dose equivalent) of  $\leq 10$  mg/day. The acceptable length of interruption will be at the discretion of the investigator.

Dose interruptions for reasons other than toxicity, such as surgical procedures, may be allowed. The acceptable length of interruption will be at the discretion of the Protocol Chair.

Patients should be assessed clinically (including review of laboratory values) for toxicity prior to, during, and after each infusion. If unmanageable toxicity due to atezolizumab occurs at any time during the study, treatment with atezolizumab should be discontinued.

Management of hepatitis/transaminitis, colitis, rash, and hypothyroidism are presented in this section as they have been observed in this study and are potentially immune related.

